## 5. Analysis Populations

Analysis populations are:

- The **Intent to treat (ITT)** population, defined as all participants who were enrolled, whether or not they started treatment.
- The **Safety** population, defined as all enrolled participants who received at least one dose of study treatment. Participants will be analysed as to the treatment they actually received regardless of given allocation.
- The **Modified intent to treat (mITT)** population, defined as all participants who were enrolled and started treatment, excluding any late screening failures.
- The **TB-specific modified intent to treat (TB-mITT)** population, defined as the mITT population with additional exclusions (see below).
- The **Per-protocol (PP)** population, defined as the TB-mITT population with additional exclusions (see below).

For ITT, mITT, TB-mITT and PP; participants will be analysed as to the treatment they were randomised to receive.

For short-term culture conversion endpoints, only the mITT population will be examined.

The TB-mITT population is unique to the TB field and is outlined here (with further details provided in [Appendix §13.3](#)). TB-mITT is a key analysis that has been used in the literature of long-term outcome trials of durable cure in TB, although it has generally been referred to simply as the ‘mITT analysis’. This analysis excludes participants based on data collected post-randomisation. A true mITT analysis, as recognised by regulatory authorities, does not exclude any participants due to missing data post-enrollment.

Thus, for the long-term endpoint of durable cure, the TB-mITT analysis will be considered primary for the purposes of publication, to allow comparison with the rest of the literature in the TB field. However, for regulatory purposes, we recognise that regulatory agencies will consider the mITT analysis primary.

## 6. Endpoint definitions

### 6.1. Short term endpoints

#### 6.1.1. mITT Population

Participant status is defined in [§3.1](#).

##### 6.1.1.1. Unassessable status (late exclusions)

1. Participants enrolled and later found to be ineligible because of a protocol violation at enrolment (based on data collected prior to enrolment).
2. Participants without culture confirmation of M.tb at Day 1 (baseline) sputum samples (or screening or out to Week 4 if the baseline is contaminated or negative). These participants will be late exclusions from the study.

### 6.2. Long term endpoints

#### Favourable status (all analysis populations)

Participants with culture negative status at the time of the endpoint (at 12 or at 24 months), who have not already been classified as having an unfavourable outcome and whose last positive culture result (“isolated positive culture”) was followed by at least two negative culture results. For participants who are missing culture status at the 12 month endpoint but who have a culture result at a future timepoint will be considered culture negative status at 12 months if both the previous and future culture results are negative.

#### 6.2.1. mITT Population

##### 6.2.1.1. Unassessable status (late exclusions)

1. Participants enrolled and later found to be ineligible because of a protocol violation at enrolment (based on data collected prior to enrolment).

2. Participants without culture confirmation of M.tb at Day 1 (baseline) sputum samples (or screening or out to Week 4 if the baseline is contaminated or negative). These participants will be late exclusions from the study.

#### **6.2.1.2. Unfavourable status**

Participants in the mITT analysis population who do not reach the time of the endpoint (12 or 24 months depending on the endpoint) or who are not culture negative status at the time of the endpoint (12 or 24 months) and whose last positive culture result (“isolated positive culture”) was not followed by at least two negative culture results.

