### **3.1.3. Culture negative status**

Culture negative status is achieved when a participant produces at least two negative culture results at different visits (at least 7 days apart) without an intervening positive culture result for M.tb. The date of the first negative culture (date of collection of culture) of these two is the date at which culture negative status was obtained. Once obtained, culture negative status continues until there are two positive cultures at different visits (at least 7 days apart), without an intervening negative culture, or until there is a single positive culture not followed by two negative cultures. Culture negative status can be achieved at any time during treatment or follow-up but before any re-treatment. Culture negative status can be re-established. A single culture result or inability to produce sputum (see [§3.1.4](#)) at 8 weeks will be sufficient to count that participant as having data for endpoint classification.

Participants with two contaminated or missing samples at a given visit (from month 2 onwards) will be asked to return to produce two more sputum samples.

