#### **6.2.2.2. Unfavourable status**

1. Participants not classified as having achieved or maintained culture negative status when last seen, or
2. Participants previously classified as having culture negative status who, following the end of treatment, have two positive cultures without an intervening negative culture (however, see [§3.1.2](#) for an exception), or
3. Participants who had a positive culture not followed by at least two negative cultures when last seen, or
4. Participants dying from any cause during treatment, except from violent or accidental cause (e.g. road traffic accident), not including suicide (e.g., suicide will be considered an unfavourable outcome), or
5. Participants definitely or possibly dying from TB related cause during the follow-up phase, or
6. Participants requiring an extension of their treatment beyond that permitted by the protocol a restart or a change of treatment for any reason except reinfection or pregnancy, or
7. Participants lost to follow up or withdrawn from the study before the end of treatment.

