## **9. Participant Disposition**

### **9.1. Participant Disposition**

Participant disposition for all participants who signed informed consent will be presented as follows:

- No. of participants screened, screen failed, randomised, and received at least one dose of treatment.

- Of those receiving at least one dose, the number and proportion who completed the IMP, who discontinued IMP, who completed the study, who discontinued from the study. The reasons for discontinuation of IMP and study participation will also be summarised.

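### The mITT outcome rule at 12 and 24 months has no treatment-change criterion, so a participant who converts, is switched to another regimen and stays culture negative is favourable in mITT but unfavourable in TB-mITT

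*SAP*

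**What the plan says.** Four parts of the SAP decide how a participant whose treatment is changed is classified at 12 or 24 months.

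- **mITT unfavourable (6.2.1.2).** Participants "who do not reach the time of the endpoint (12 or 24 months depending on the endpoint) or who are not culture negative status", judged at the endpoint, and whose last positive culture was not followed by two negatives. Extension, restart or change of treatment does not appear.
- **TB-mITT unfavourable (6.2.2.2, item 6).** Extension beyond what the protocol permits, "a restart or a change of treatment for any reason except reinfection or pregnancy". Section 6.2.3.2 takes points 1 to 6 over into PP.
- **Favourable, all populations (6.2).** Culture negative at the endpoint, for those "who have not already been classified as having an unfavourable outcome and whose last positive culture result" was followed by at least two negatives. Being on the allocated regimen is not required.
- **Culture negative status (3.1.3).** On gaining it, the section says: "Culture negative status can be achieved at any time during treatment or follow-up but before any re-treatment". On losing it, the rule is different: "Once obtained, culture negative status continues until there are two positive cultures at different visits", or until a single positive is not followed by two negatives. A change of treatment does not end it.

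On the standing of mITT, section 5 says that for the long-term endpoint "for regulatory purposes, we recognise that regulatory agencies will consider the mITT analysis primary", while TB-mITT is primary for publication.

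**The concern.** The mITT rule looks at whether the participant got to the endpoint and at the cultures, never at the treatment that produced them. A cure obtained with a replacement regimen can therefore be credited to the allocated one. In a non-inferiority comparison this pulls the arms together if switching is commoner on the experimental regimen, because those participants leave the unfavourable count.

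Nothing inside mITT would show it. Both sensitivity analyses in section 7.2.1.2 concern reinfections and deaths, and both use TB-mITT and PP only. At stake is the non-inferiority result in the analysis that the SAP expects regulators to rely on for durable cure. The 12-month outcome is the key secondary endpoint (2.2) and becomes the primary one if recruitment is extended after the interim analysis (7.3.1).

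**Working it through.** **Step 1. Follow the cases through the rules.**

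| Participant | mITT | TB-mITT |
|---|---|---|
| A. Converts at week 4, stops the allocated regimen at week 8 for an adverse reaction, takes another TB regimen, stays in follow-up, culture negative at month 12 | Favourable: status gained before the switch and never ended (3.1.3, 6.2) | Unfavourable (6.2.2.2 item 6) |
| B. Taken off treatment and does not reach the endpoint | Unfavourable (6.2.1.2) | Depends on timing and last status |
| C. Re-treated before converting, or after losing status, then gives negative cultures to month 12 | Not favourable, since 3.1.3 does not let status be gained after re-treatment. Also not clearly unfavourable: the endpoint was reached, and the last positive was followed by two negatives, so the condition joined by *and* fails | Unfavourable (item 6) |

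Case A is the point. Case C is a related gap, in which a participant may fall into neither mITT category. In PP, case A is either excluded (6.2.3.1 item 2) or unfavourable, but not favourable.

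Section 3.2 includes being re-treated, or changing from protocol treatment, for TB in its definitions of failure and relapse. Section 6.2.1.2 does not refer to it.

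**Step 2. Reproduce the plan's own figures (section 4, 7.3.3 and Appendix 13.4).** Inputs: 16% unfavourable, 13% unassessable, margin 12 points, one-sided 2.5%, true difference 0.

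- Evaluable per arm: 150 × 0.87 = 130.5. SE = √(2 × 0.16 × 0.84 / 130.5) = 0.0454. Power = Φ(0.12/0.0454 − 1.96) = Φ(0.68) = 75.3%, against 74% stated.
- For 90% power: n = (1.960 + 1.282)² × 2 × 0.1344 / 0.12² = 196.1, so 197 rounded up (196 stated); 197 / 0.87 = 226.4, so 227 (225 stated).

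Both agree closely, so the inputs are suitable for setting the scale.

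**Step 3. Effect on the upper bound.** Let s be the net excess, 4BPaMZ minus control, of case A participants. The SAP gives no value, so s is an assumption. The base p is the unfavourable proportion in each arm apart from case A. As written, case A is ignored and the difference is 0. With case A counted, pE = p + s and pC = p. The unadjusted Wald bound is

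U = s + 1.96 × √[pC(1 − pC)/n + pE(1 − pE)/n].

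| n per arm | Base p | As written (s = 0) | s = 2 | s = 3 | s = 4 | s = 5 |
|---|---|---|---|---|---|---|
| 225 | 16% | 6.8 | 8.9 | 10.0 | 11.1 | 12.2 |
| 150 | 16% | 8.3 | 10.5 | 11.6 | 12.7 | 13.8 |
| 225 | 29% | 8.4 | 10.5 | 11.5 | 12.5 | 13.6 |
| 150 | 29% | 10.3 | 12.4 | 13.4 | 14.5 | 15.5 |

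Example, n = 225, p = 16%, s = 5: 5 + 1.96 × √[(0.1344 + 0.1659)/225] × 100 = 5 + 7.2 = 12.2. The 29% rows add the 13% unassessable to the 16%, because mITT counts those who do not reach the endpoint as unfavourable.

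**Step 4. Effect on the error rate.** Suppose the true difference with case A counted is exactly 12 points, control is 16% and s = 4. The rule as written then sees pE = 24%, a difference of 8 points. The chance of declaring non-inferiority is Φ(0.04/SE − 1.96):

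- 150 per arm: SE = 0.0460, giving Φ(−1.09) = 13.8%.
- 225 per arm: SE = 0.0375, giving Φ(−0.89) = 18.6%.

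It would be 2.5% if case A were counted.

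**The case against.** The strongest reply is that classifying by end status whatever happened to treatment is a recognised treatment-policy approach for an intention-to-treat type of set, and that the alternative is already planned. Section 2.2 runs the comparison in mITT, TB-mITT and PP, and the last two handle switches differently. Section 6 openly gives each population its own outcome rule, so a different result by population is not in itself a contradiction. This stands in part: the current rule is defensible as a strategy. But the SAP never says that it is one, and section 3.2 points the other way.

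It is also fair that the scenario depends on follow-up after treatment stops. Section 9.1 tabulates those "who discontinued IMP, who completed the study, who discontinued from the study" as separate counts, and section 1 says that all participants are followed for 2 years. Both suggest that switched participants can reach month 12, but section 3.2 describes TB-related switches as a kind of withdrawal. If all switched participants leave the study, they are already unfavourable. How often case A arises is therefore unknown.

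A reader might infer that anyone taken off 4BPaMZ counts as a 4BPaMZ success. The documents do not support that. It requires conversion before the switch, status kept throughout and follow-up to the endpoint. Nor is the direction of bias given: the rule is the same in both arms, and the SAP states no switch rate for either.

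**Conclusion.** The point holds for a defined group: participants in either arm who converted, were then moved to another TB regimen, stayed in follow-up and kept culture negative status. They are favourable in mITT and unfavourable in TB-mITT, and the SAP neither explains the difference nor tests it within mITT. A smaller group, re-treated before converting or after losing status, may have no mITT category.

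The size depends on an assumed excess of switching on 4BPaMZ. With a 16% base it takes about 5 points at 225 per arm, or about 4 at 150 per arm, to move the upper bound past the margin; with a 29% base it takes about 4 and 2 points. Smaller excesses leave the conclusion unchanged in this illustration, and equal switching gives no net shift. The bounds are unadjusted, whereas section 7 plans adjustment for HIV status and cavitation.

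This is a should-fix. The endpoint is key secondary unless the trial expands, and TB-mITT and PP already offer another view, but the rule can alter the result in the analysis expected to be primary for regulators on durable cure.

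**What to change.** 1. Add to 6.2.1.2 the outcome-classification criterion of 6.2.2.2 item 6: extension beyond that permitted by the protocol, restart, or change of treatment before the endpoint. Apply it to both arms and date it at the event, which section 7.2.3 needs for time to unfavourable status.
2. State explicitly how the reinfection and pregnancy exceptions apply in mITT. TB-mITT excludes those participants under 6.2.2.1, whereas mITT keeps them and must give them a category. Wording that covers a change for any reason, with no mention of the exceptions, would silently drop them.
3. Reconcile the criterion with 3.1.3 and 3.2. Say whether a switch during treatment is re-treatment for the purpose of gaining culture negative status, and make sure that every mITT participant falls into exactly one category.
4. Report the opposite classification, culture status regardless of treatment change, as a labelled mITT sensitivity analysis.

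This concerns how outcomes are counted, not when treatment may be changed. The cost is a few sentences in the SAP and one extra analysis, using data that item 6 already requires for TB-mITT. The downside is a slightly higher mITT unfavourable proportion.

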#### **6.2.2. TB-mITT Population**

##### **6.2.2.1. Unassessable status (additional exclusions from mITT)**

In addition to those excluded from the mITT analysis (see §6.2.1.1), the following participants will be excluded:

1. Participants who, having completed treatment, are lost to follow-up or withdrawn from the study, their last status being culture negative and their last positive culture result (“isolated positive culture”) followed by at least two negative culture results at different visits (at least 7 days apart, without an intervening positive culture).
2. Women who become pregnant during treatment and stop their allocated treatment.
3. Participants with suspected/confirmed COVID-19 during treatment and who stop their allocated treatment.
4. Participants who died during treatment from violent or accidental cause (e.g. road traffic accident). N.B.: This does not include death from suicide, which will be considered an unfavourable outcome.
5. Participants who died during follow-up (after the end of treatment) with no evidence of failure or relapse of their TB, their last status being culture negative and their last positive culture result (“isolated positive culture”) followed by at least two negative culture results at different visits (at least 7 days apart).
6. Participants who, after being classified as having culture negative status are deemed culture positive and are infected with a new strain that is different from that with which they were originally infected. Reinfection will be defined specifically as a participant infected with a strain that is genetically different from the initial strain (see [Appendix §13.2](#)).

7. Participants who are able to produce sputum at the endpoint visit, but whose endpoint visit sputum samples are all contaminated or missing, who cannot be brought back for repeat cultures, provided their last positive culture was followed by at least two negative cultures. N.B.: This does not apply to participants who are unable to produce sputum at the given endpoint (see [§3.1.4](#)), or to participants who are able to be brought back subsequently and produce negative cultures.

Participants in categories 1-7 above who have already been classified as having an unfavourable outcome will not be excluded.

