### **3.2. Bacteriological failure, Relapse or Reinflection**

**Treatment failure** is defined as being declared an unfavourable outcome at or before the end of treatment (either 4 or 6 months) or failing to attain culture negative status and being declared an unfavourable outcome ([§6.2](#)) or the participant is withdrawn at or before the end of treatment for clinical (TB) reasons including being re-treated (or changing from protocol treatment) for TB.

**Relapse or bacteriological relapse** is defined as failing to maintain culture negative status or being declared an unfavourable outcome ([§6.2](#)) after the end of treatment (either 4 or 6 months) in those participants who attained culture negative status by the end of treatment and had culture conversion to positive status with an M.tb strain that is genetically identical to the infecting strain at baseline or after the end of treatment in those participants who attained culture negative status by the end of treatment and were withdrawn for clinical (TB) reasons, including being re-treated (or changing from protocol treatment) for TB. Details are given in [Appendix §13.2](#).

**Reinfection or bacteriological reinfection** is defined as failing to maintain culture negative status or being declared an unfavourable outcome (including being withdrawn for clinical (TB) reasons including being re-treated or changing from protocol treatment for TB) after the end of treatment in those participants who attained culture negative status by the end of treatment and had culture conversion to positive status with a M.tb strain that is genetically different from the infecting strain at baseline. If reinfection cannot be distinguished from relapse, the participant will be assumed to have relapsed. A single positive sample will be sufficient for strain typing to compare to baseline. Full details are in [Appendix §13.2](#).

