#### **6.2.3. PP Population**

##### **6.2.3.1. Unassessable status (additional exclusions from TB-mITT)**

In addition to those already excluded from the mITT (see [§6.2.1.1](#)) and the TB-mITT (see [§6.2.2.1](#)) analyses, the following participants will be excluded from the PP analysis:

1. Participants lost to follow-up or withdrawn for reasons other than treatment failure (e.g. participant consent or relocation) before the end of treatment, unless they have already been classified as having an unfavourable outcome.

2. Participants whose treatment was modified or extended beyond what is permitted in the protocol for reasons other than an unfavourable therapeutic response to treatment (e.g. an adverse drug reaction), unless they have already been classified as having an unfavourable outcome.
3. Participants not meeting the definition of having received an adequate amount of their allocated study regimen (see §3.3), provided this is not due to an unfavourable outcome.
4. Participants who are classified as “major protocol deviations for analysis” (see §3.5), unless they have already been classified as having an unfavourable outcome on the basis of data obtained prior to the protocol deviation

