#### **6.2.3.2. Unfavourable status**

Points 1-6 in §6.2.2.2 Unfavourable status in the TB-mITT Population section above

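### TB-mITT exclusion 1 lacks a no-relapse condition, so a culture-negative clinical relapse withdrawn after treatment without re-treatment can drop out of TB-mITT and PP

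*SAP*

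**What the plan says.** Section 3.2 of the SAP defines relapse after the end of treatment. One limb covers participants who were culture negative by the end of treatment "and were withdrawn for clinical (TB) reasons, including being re-treated (or changing from protocol treatment) for TB".

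Section 6.2.2.1 lists who leaves TB-mITT as unassessable. Item 1 is "Participants who, having completed treatment, are lost to follow-up or withdrawn from the study, their last status being culture negative", provided any last positive culture was followed by at least two negatives. It does not mention the reason for withdrawal. Item 5 covers deaths in follow-up; it sets the same culture conditions and also requires that nothing points to failure or relapse. The list closes with an override: "Participants in categories 1-7 above who have already been classified as having an unfavourable outcome will not be excluded".

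Section 6.2.2.2 lists the unfavourable outcomes. Item 6 includes participants requiring "a restart or a change of treatment for any reason except reinfection or pregnancy". Item 7 is "Participants lost to follow up or withdrawn from the study before the end of treatment".

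PP inherits the TB-mITT exclusions (section 6.2.3.1). It takes as unfavourable "Points 1-6 in §6.2.2.2 Unfavourable status in the TB-mITT Population section above".

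Section 6.2.1.2 counts as unfavourable in mITT anyone who does not reach the endpoint. Section 5 makes TB-mITT primary for publication and expects regulators to treat mITT as primary.

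**The concern.** The same participant can be a relapse under section 3.2 and unassessable under section 6.2.2.1. Relapse is what a comparison of a 4-month with a 6-month regimen most needs to detect. A rule that removes some relapses from two of the three populations used for non-inferiority therefore deserves attention even if it applies rarely. Exclusion 5 shows that the authors saw that a culture-negative last status does not by itself rule out relapse. They wrote that safeguard for deaths but not for withdrawals. Neither sensitivity analysis in section 7.2.1.2 (reinfections, deaths) would bring the withdrawn cases back.

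**Working it through.** **Step 1: follow one participant through the text.** Take someone who completes treatment, is culture negative when last seen, and is withdrawn before month 12 because the investigator judges that TB has returned clinically. No restart or change of treatment has happened by then.

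- Section 3.2: relapse, because re-treatment is introduced only as an included example.
- Section 6.2.2.2, items 1 to 3: not met; they need culture evidence.
- Items 4 and 5: not met; they need a death.
- Item 6: met only if this participant counts as requiring a restart or change.
- Item 7: not met; it stops at the end of treatment.
- Section 6.2.2.1, item 1: met.
- Override: applies only if an unfavourable item was already met. If item 6 is read as needing actual re-treatment, none was. If re-treatment starts after withdrawal, the text does not say whether the participant was already classified.
- Result: can be excluded from TB-mITT and hence from PP; unfavourable in mITT (section 6.2.1.2).

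**Step 2: reproduce the plan's figure.** Inputs from section 4: 150 per arm, 16% unfavourable, 13% unassessable, margin 12%, two-sided 5%.

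- Assessable per arm: 150 × 0.87 = 130.5.
- SE = √(2 × 0.16 × 0.84 / 130.5) = 0.0454.
- Power = Φ(0.12/0.0454 − 1.96) = Φ(0.684), about 75%, against 74% stated. This is close enough to use 130 per arm below.

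**Step 3: effect of one dropped case.** Dropping k unfavourable cases from a/n lowers the rate by a/n − (a−k)/(n−k) = k(n−a)/[n(n−k)]. With n = 130 and a = 21 (0.16 × 130 = 20.8):

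- k = 1: 21/130 − 20/129 = 0.65 points
- k = 2: 21/130 − 19/128 = 1.31 points
- k = 3: 21/130 − 18/127 = 1.98 points

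The reduction shrinks as a grows. When the 4BPaMZ rate is at or above the control rate, equal losses therefore do not narrow the difference. It narrows only if more cases are lost from 4BPaMZ.

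**Step 4: a borderline result (assumed counts, unadjusted Wald limit).**

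- 25/130 v 21/130: difference 3.08 points, upper limit 12.35%, fails.
- One case dropped from 4BPaMZ only, 24/129 v 21/130: upper limit 11.68%, passes.
- One case dropped from each arm, 24/129 v 20/129: upper limit 12.27%, still fails.

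**Step 5: error rate at the margin.** True rates are 16% v 28% with 130 per arm. A fraction of each arm moves from unfavourable to excluded. The chance that the upper 95% limit falls below 12%, by normal approximation, is:

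| Lost from control | Lost from 4BPaMZ | Chance of declaring non-inferiority |
|---|---|---|
| 0 | 0 | 2.5% |
| 1% | 1% | 2.4% |
| 2% | 2% | 2.2% |
| 0.5% | 1% | 2.9% |
| 1% | 2% | 3.3% |
| 0 | 1% | 3.5% |
| 0 | 2% | 4.7% |

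Every loss fraction here is an assumption; the SAP gives none.

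**The case against.** The case for leaving the text alone has four parts.

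- **Item 6 may already cover the case.** It turns on what a participant requires, not on what was recorded. Someone withdrawn because TB has returned can naturally be said to require a restart, and the override would then keep them in. This reading is reasonable and probably captures most clinical relapses. It is not the only reading, and it does not settle re-treatment that starts after withdrawal.
- **Section 3.2 may only label outcomes.** Its sentence is loosely built. The clinical-withdrawal limb could attach to the opening words about outcomes already declared unfavourable under section 6.2. That parse is possible, but it still leaves section 6.2 without a criterion for the event.
- **mITT is unaffected.** The comparison is also run in mITT, where these participants count as unfavourable. This stands in full.
- **Exclusion 1 applies to both arms.** Equal losses give 2.4% or 2.2%, slightly below the nominal 2.5%. This also stands: the 3.5% and 4.7% figures need control to lose no case at all.

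A reader might also infer a second gap in PP. Section 6.2.3.1 excludes participants "withdrawn for reasons other than treatment failure (e.g. participant consent or relocation) before the end of treatment", which leaves withdrawals for treatment failure in, while section 6.2.3.2 omits item 7. The person concerned would have to be culture negative, withdrawn for treatment failure, and yet not require a change of treatment. That is close to an empty set and does not support a separate finding.

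**Conclusion.** The mismatch is real but narrow. As written, exclusion 1 can remove from TB-mITT and PP a culture-negative clinical relapse that was withdrawn without re-treatment, or re-treated only after withdrawal.

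A reader might infer that every culture-negative withdrawal for clinical TB is lost, or that relapses leave the non-inferiority analysis altogether. The documents support neither. Item 6 and the override keep relapses requiring re-treatment, and mITT keeps everyone who does not reach the endpoint as unfavourable.

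Nor can a reader conclude that the plan is biased toward non-inferiority by a known amount. The number of such cases and their split by arm are not in the SAP. Such bias needs a net loss from 4BPaMZ, given a 4BPaMZ rate at or above control's. The group is probably small, but in a borderline result a single case lost from 4BPaMZ alone could change the TB-mITT or PP conclusion.

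**What to change.** Three changes to the SAP wording:

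1. In section 6.2.2.1, item 1, add the condition that exclusion 5 already carries, that there is no evidence of TB failure or relapse, with a cross-reference to section 3.2.
2. In section 6.2.2.2, state that withdrawal for clinical (TB) reasons as defined in section 3.2, other than reinfection, is unfavourable. Have section 6.2.3.2 import that item.
3. Classify the reason for each withdrawal blind to arm before database lock, alongside the lists already planned in sections 3.4 and 3.5.

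The cost is the text change and one more blinded list. The unfavourable proportion in TB-mITT and PP may rise slightly in either arm. No sample size or power figure in the SAP has to change.

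### In TB-mITT, the COVID-19 exclusion conflicts with unfavourable items 6 and 7 for some participants who stop treatment, and it does not require COVID-19 to be the reason for stopping

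*SAP*

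**What the plan says.** SAP §6.2.2.1 lists seven groups removed from the TB-mITT analysis in addition to the mITT exclusions. Exclusion 3 reads "Participants with suspected/confirmed COVID-19 during treatment and who stop their allocated treatment". Exclusion 2 has the same form: "Women who become pregnant during treatment and stop their allocated treatment". The list closes with a protective sentence: "Participants in categories 1-7 above who have already been classified as having an unfavourable outcome will not be excluded".

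SAP §6.2.2.2 defines unfavourable status in the same population. Item 6 covers treatment extended past the protocol limit and also "a restart or a change of treatment for any reason except reinfection or pregnancy". Item 7 covers "Participants lost to follow up or withdrawn from the study before the end of treatment". Item 1 covers those without culture negative status when last seen.

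The PP population (§6.2.3) takes over the TB-mITT exclusions, adds its own, and uses unfavourable items 1 to 6. The mITT definitions (§6.2.1) contain no COVID-19 exclusion. Section 5 makes TB-mITT primary for publication of the long-term endpoint and recognises that regulators will treat mITT as primary.

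**The concern.** Item 6 gives a closed list of exceptions. Reinfection and pregnancy appear in it, matching exclusions 6 and 2. COVID-19 does not, although exclusion 3 treats it in the same way as pregnancy. The version history records a COVID clause added at version 2.1, which would be consistent with item 6 not having been updated to match. Two programmers could classify the same participant differently and both comply with the SAP.

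The second gap is the scope of exclusion 3. It needs COVID-19 during treatment and a stop, but no link between them, and suspected COVID-19 is enough. Exclusions 1, 5 and 7 require that the last positive culture was followed by at least two negatives; exclusion 3 has no such condition. A participant with suspected COVID-19 who changes treatment for an unrelated reason can therefore be dropped, while the same change without COVID-19 is unfavourable.

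At stake is the 12-month non-inferiority comparison in TB-mITT. This is the key secondary endpoint, and §7.3.1 makes it primary if the sample is expanded. Allocation is open (§1.2). The SAP provides arm-blind review for deaths (§3.4) and major deviations (§3.5) but states none for exclusion 3. The two sensitivity analyses in §7.2.1.2 reclassify reinfections and deaths; neither restores surviving participants removed under exclusion 3.

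**Working it through.** **Step 1. The rules set side by side, for a participant with COVID-19 during treatment who stops allocated treatment (TB-mITT)**

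| What happens | Exclusion 3 | Unfavourable list | Settled by the protective sentence? |
|---|---|---|---|
| Already classified unfavourable before the stop | met | met | Yes: kept as unfavourable |
| Stays in follow-up, culture negative, no further treatment | met | no item met | No conflict: excluded |
| Restarts, changes or over-extends treatment | met | item 6 | No |
| Lost or withdrawn from the study before end of treatment | met | item 7 | No |
| Fails or relapses after the stop | met | items 1, 2 or 3 | No |

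In the last three rows the outcome turns on the word *already*. If the change, withdrawal or later failure counts as the classification, those participants stay in and exclusion 3 is left with little beyond the second row. If it does not, exclusion 3 overrides items 6 and 7 without saying so.

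**Step 2. The plan's own figures**

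Inputs from SAP §4: 150 per arm, 16% unfavourable, 13% unassessable, margin 12%, two-sided 5%. Analysed per arm: 150 × 0.87 = 130.5.

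Power = Φ(0.12 / √(2 × 0.16 × 0.84 / 130.5) − 1.96) = 75.3%, against the stated 74%. For the expanded design, the same approximation at 90% power gives 197 analysed per arm against 196 in Appendix 13.4, and 196 / 0.87 = 225.3 against the stated 225. The design figures reproduce and are not in dispute.

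**Step 3. Weight of one participant**

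Moving k participants in an arm from excluded to unfavourable changes its rate by (0.16n + k)/(n + k) − 0.16. For k = 1 this is 0.64 point at n = 130 and 0.43 point at n = 196.

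**Step 4. Effect on the error rate (assumed counts)**

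The SAP gives no number of COVID-19 stoppers, so k from 0 to 5 is an assumption. Set the true difference at the margin (28% against 16%) and remove k failures from the intervention arm only:

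- intervention rate a = (0.28n − k)/(n − k); control rate c = 0.16; difference d = a − c
- SE = √(a(1 − a)/(n − k) + c(1 − c)/n)
- false non-inferiority rate = Φ((0.12 − d)/SE − 1.96)

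Example, n = 130 and k = 3: a = 33.4/127 = 0.263, d = 0.103, SE = 0.0506, rate = Φ(0.336 − 1.96) = 5.2%.

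| k removed, intervention arm only | 0 | 1 | 2 | 3 | 5 |
|---|---|---|---|---|---|
| Difference, n = 130 (points) | 12.0 | 11.4 | 10.9 | 10.3 | 9.1 |
| False non-inferiority, n = 130 | 2.5% | 3.2% | 4.1% | 5.2% | 8.3% |
| False non-inferiority, n = 196 | 2.5% | 3.1% | 3.8% | 4.6% | 6.7% |

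Removing 5 failures from each arm gives 2.0% at n = 130 and 2.1% at n = 196, so balanced removal does not inflate the error.

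**The case against.** The strongest reply is that this is a narrow drafting gap with safeguards around it. Much of that stands.

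- A reader might infer that every participant with COVID-19 who stops treatment is both excluded and unfavourable. The text does not say so. No item in §6.2.2.2 makes a stop unfavourable in itself, and item 7 concerns leaving the study, not stopping treatment. For the same reason, a bare stop for toxicity without COVID-19 is not unfavourable either.
- A reader might infer that COVID-19 deaths on treatment are left open. Item 4 counts on-treatment deaths from any cause other than violence or accident, and the second sensitivity analysis treats all deaths as unfavourable in TB-mITT and PP.
- Failures classified before the stop are kept by the protective sentence.
- The mITT analysis has no such exclusion, so it provides a check. In PP, the exclusions for early loss or withdrawal, modified treatment and inadequate treatment would remove many of these participants anyway, and item 7 is not used.
- Exclusion 2 for pregnancy also lacks a stated reason for stopping. That is true, but item 6 contains the pregnancy exception, so the contradiction with item 6 is specific to COVID-19.
- A reader might suspect that open allocation would be used to label stops as suspected COVID-19. Nothing in the document shows differential use; the point is only that no arm-blind check is stated.

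These points limit the scope. They do not say which rule prevails in the last three rows of the table, and they do not supply the missing reason-for-stopping condition.

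**Conclusion.** The SAP is wrong as written on a limited point. In TB-mITT, and to a lesser extent in PP, exclusion 3 conflicts with items 6 and 7 for a participant with COVID-19 who stops and then restarts, changes or over-extends treatment, or leaves before the end of treatment. The order of precedence is also unstated for a failure after the stop. Because exclusion 3 has no reason or culture condition, such participants can be dropped instead of counted as unfavourable.

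The size is unknown. The rise from 2.5% to 3.2–8.3% at 130 per arm (3.1–6.7% at 196) assumes 1 to 5 true failures removed, all from the intervention arm, with the true difference at the margin. Inflation requires removals that differ between arms. It would go too far to conclude that the trial's non-inferiority result as a whole is compromised: mITT does not use this rule. The exposure is mainly in the analysis named as primary for publication.

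**What to change.** 1. Limit exclusion 3 in §6.2.2.1 to stops for which COVID-19 is the recorded reason, confirmed by a review blind to arm, as §§3.4 and 3.5 already provide for deaths and major deviations.
2. Add the matching COVID-19 exception to item 6 of §6.2.2.2. State whether exclusion 3 or item 7 prevails for loss or withdrawal, and how a failure after the stop is classified.
3. Add to §7.2.1.2 a TB-mITT sensitivity analysis that counts all exclusion-3 participants as unfavourable.

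The cost is SAP wording, a blinded check of the reason for stopping, and one extra run.
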